11.2. Participant Stopping Rules and Withdrawal Criteria

Participants may be prematurely terminated from the study for the following reasons:

1. The participant elects to withdraw consent from all future study activities, including follow-up.
2. The participant is “lost to follow-up” (i.e., no further follow-up is possible because attempts to reestablish contact with the participant have failed).
3. The participant dies.
4. The Investigator no longer believes participation is in the best interest of the participant.
5. The study is stopped by the site, the sponsor (NIAID), or the Food and Drug Administration.

11.3. Participant Replacement

Participants who withdraw or are withdrawn will not be replaced if they have received at least one dose of rituximab.

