Retransplantation	Listed for a second lung transplant
Protocol Mandated Procedures	Any procedure performed solely for the purpose of this research study (not site-specific standard of care)
Randomized	A subject who met all eligibility criteria (inclusion and exclusion); met with the study investigator or designee to discuss the study purpose, requirements (i.e., time requirements, schedule of events, etc.), discussed all risks and benefits, and signed the informed consent document.
Study Termination	The subject will no longer be seen for any study related procedure; including clinical assessments, local laboratory assessments, study therapy, core mechanistic studies. No data will be submitted on any subject as of the date of termination.
Study Therapy	The investigational agent and all protocol required therapies include the following; Rituximab (Rituxan®) or Rituximab Placebo, Standard of Care Immunosuppression (Thymoglobulin® (induction), Tacrolimus, Mycophenolate Mofetil and corticosteroids).

1. Study Hypothesis/Objectives

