Individuals who meet the criteria listed below will not participate in the phone calls for the tacrolimus standard deviation marker:

1. Inpatient status
2. Any condition that, in the opinion of the investigator, may impact the quality or interpretation of the data obtained from the intervention.

The frequency of the calls is described in the table below.

Timepoint (following SD of 2.0 or more or undetectable level)	Call Frequency
Month 1	Weekly
Month 2	Monthly
Month 3-Month 24	Every other month

Table 10: Tacrolimus Standard Deviation Marker Call Schedule

Per the center clinician's discretion, calls may be escalated to 2 times per week for up to 1 month at any time during the intervention.

After one month, calls may revert to a weekly schedule for the following reasons:

- Participant discloses continuing non-adherence during the call;
- The most recent trough level is “undetectable”;
- The parent/guardian and/or team are concerned about ongoing non-adherence;
- A deterioration in medical outcomes as determined by the Center that is not explained by physiological factors;
- Per the clinical discretion of the call center staff member (i.e., the call center and parents/guardians are working on a remedy to an identified barrier).

The team at the call center will determine when the participant will return to the schema outlined in **Table 10**.

With the consent of the participant, information obtained during the intervention will be shared with the participant’s parent(s)/guardian(s) and clinical team.

Neurological Assessment

All participants who receive at least 1 dose of Rituximab (Rituxan®) or placebo will undergo a screening neurological exam at the time points specified in Appendix 1. Subjects who have objective findings will be evaluated by their local Neurology consult service.

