11.4. Follow-up after Early Study Withdrawal

Participants who receive at least one dose of rituximab will follow the schedule of events-Appendix 1.

12. Safety Monitoring and Reporting

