13.4.1 Analysis Populations

Intent-to-Treat (ITT) Sample. All randomized subjects who receive at least a portion of the initial rituximab/placebo infusion will constitute the ITT sample. This sample will be used for evaluation of the primary and secondary clinical endpoints. Subjects will be analyzed in the group to which they were randomized, regardless of compliance with the protocol or withdrawal from the study.

Per-Protocol (PP) Sample. Subjects from the ITT sample who complete the full induction protocol, with complete administration of the prescribed dose at both the initial and subsequent infusions, will make up the PP sample. This sample will capture subjects who both tolerate rituximab well and recover as expected from their transplant.

Safety Sample. All subjects from the ITT sample will constitute the safety sample.

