4. ANALYSIS SAMPLES

Intent-to-Treat (ITT) Sample – The ITT sample is all randomized subjects who receive at least a portion of the initial rituximab/placebo infusion. This sample will be used for evaluation of the primary and secondary clinical endpoints. Subjects will be analyzed in the group to which they were randomized, regardless of compliance with the protocol or withdrawal from the study.

Per-Protocol (PP) Sample – The PP sample is the subset of subjects from the ITT sample who complete the full induction protocol, with complete administration of the prescribed dose at both the initial and subsequent infusions, and do not have any major protocol deviations that impact the subject’s evaluability for the primary endpoint. This sample will capture subjects who both tolerate rituximab well and recover as expected from their transplant.

Screening Sample – All consented (i.e., enrolled) subjects will constitute the screening sample. This sample will be used to describe population characteristics.

Safety Sample – All subjects from the screening sample who have the pre-transplant blood draw performed will constitute the safety sample. This sample will be used for all safety summaries. Subjects in this sample who were randomized will be analyzed in the group to which they received, regardless of which group they were randomized to, compliance with the protocol, or withdrawal from the study. If a subject received any rituximab the subject will be analyzed with the rituximab group.

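### The Study Termination definition ends endpoint data for children who have not withdrawn consent, against the protocol's own follow-up rules; 11.3 and 11.4 should also name study drug, not rituximab

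*Protocol*

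**What the plan says.** The Study Definitions page of the protocol, under Study Termination, ends all study contact and adds: "No data will be submitted on any subject as of the date of termination". Section 11.2 lists the reasons for early termination. Besides withdrawn consent and death, they include loss to follow-up (item 2) and the investigator's view that participation no longer serves the child (item 4). The Lost to Follow-Up definition leaves that decision to the site PI, after at least three consecutive missed visits and unsuccessful phone contacts.

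Other sections expect data to continue:
- Section 11.4, on follow-up after early withdrawal: "Participants who receive at least one dose of rituximab will follow the schedule of events-Appendix 1".
- Sections 12.4.1 and 12.4.3 collect and follow adverse events until 30 days after withdrawal where consent stands.
- Section 8.4 collects chronic allograft dysfunction (CAD), relisting and death up to 54 months.
- Section 13.4.1 analyses ITT subjects "regardless of compliance with the protocol or withdrawal from the study".

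On replacement, section 11.3 says: "Participants who withdraw or are withdrawn will not be replaced if they have received at least one dose of rituximab". The ITT sample has a different trigger. Protocol 13.4.1: "All randomized subjects who receive at least a portion of the initial rituximab/placebo infusion will constitute the ITT sample". SAP section 4 agrees: "The ITT sample is all randomized subjects who receive at least a portion of the initial rituximab/placebo infusion".

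**The concern.** CAD, relisting and death are the three components of the primary endpoint. A child whom the investigator takes out of the study may reach one of them months later. Under the termination definition that event is never submitted. SAP 7.2.1 counts anyone without a reported death date as not having met the death component and censors at the last known status, so the child enters the Cox model as event-free up to that point. If children are terminated because they are doing badly, the censoring carries information about prognosis, which the model assumes it does not. With about 20 events expected, each one counts.

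The wording of 11.3 and 11.4 is a second, smaller matter. Both refer only to rituximab, while section 8.4 names both arms for the neurological examination: "All participants who receive at least 1 dose of Rituximab (Rituxan®) or placebo". Site clinical staff are blinded (3.5, 8.7.2), so they cannot tell which dosed children meet a rituximab-only condition.

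**Working it through.** **Step 1. Which rule applies to a dosed child terminated under 11.2 item 4, consent intact?**

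| Source | Data after that date |
|---|---|
| Study Definitions, Study Termination | None |
| 11.4 | Full Appendix 1 schedule |
| 12.4.1, 12.4.3 | Adverse events for 30 days |
| 8.4 | CAD, relisting and death to 54 months |
| 13.4.1 | Stays in ITT despite withdrawal |

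The first row cannot stand with the next three. It does not remove the child from ITT, but it removes the data that an analysis regardless of withdrawal would use.

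**Step 2. Do the triggers match?** Sections 11.3 and 11.4 require at least one dose of rituximab. ITT requires any portion of the first infusion, rituximab or placebo. Even if rituximab is read as study drug, a child whose first infusion was stopped part-way is in ITT but may not have had one dose, so it is unclear whether 11.3 and 11.4 apply.

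**Step 3. How many events are involved?** The plan states no dropout rate or allowance, so there is no planned figure to reproduce. Inputs:
- 25 + 25 children and a control rate of 74% at one year and 53% at two years (13.6), read as event-free because it falls with time.
- HR 0.40, one of the two planning values (13.6).
- Follow-up uniform over 1 to 4.5 years: an assumption based on the stated study duration.
- Dropout of 10% or 20%, each at a time uniform over the child's own follow-up: an assumption.

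Weibull fit: H(t) = λt^k, with λ = −ln 0.74 = 0.3011, H(2) = −ln 0.53 = 0.6349 and k = ln(0.6349/0.3011)/ln 2 = 1.076.

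Expected events per arm = 25 × the average over follow-up C of [1 − exp(−HR·H(C))]. This gives 14.19 on control and 7.38 on rituximab, in total 21.57. If every child dropped out, the total would be 7.97 + 3.80 = 11.77. For a dropout fraction p, events = (1 − p) × 21.57 + p × 11.77:

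| p | Events | Lost |
|---|---|---|
| 0 | 21.6 | – |
| 0.10 | 20.6 | 1.0 (5%) |
| 0.20 | 19.6 | 2.0 (9%) |

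The standard error of log HR grows by about √(21.57/19.61) = 1.05 at 20%. This is lost precision. Uniform dropout says nothing about bias.

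**Step 4. Could the censoring bias the estimate?** In an illustrative Cox simulation (25 + 25, 1,000 runs per cell, withdrawal in the first half-year), withdrawers were given three times the hazard, an assumed value, and were lost under the same rule in both arms. With a true HR of 1.00 the average estimate was 0.98, 0.98 and 1.02 at 4%, 12% and 20% withdrawal. With a true HR of 0.45 it was 0.44, 0.43 and 0.43, against 0.45, 0.46 and 0.47 when all children were followed. Loss in both arms therefore left the null in place and shifted a real effect modestly, and only under this assumed link between withdrawal and prognosis.

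**The case against.** A reader might infer something stronger from 11.3 and 11.4: that placebo children who withdraw are replaced and dropped while rituximab children are followed, so that follow-up differs by arm and the hazard ratio is biased. The documents do not support this. The protocol often writes rituximab for study drug. In 6.1.1.3 the second-dose stopping list opens with rituximab, but item 6 says placebo or rituximab. Section 6.1.2.1, on the placebo, speaks of rituximab being supplied, and 12.3.1 times cytopenia collection from the first rituximab infusion. Blinded clinical staff could not apply a one-arm rule. Sections 11.1 and 6.5 are neutral between arms, and so is the termination clause. One-arm loss would matter: with the assumed threefold hazard it moved a true HR of 1.00 to 1.11 at 12% withdrawal and 1.18 at 20%. Nothing shows that such loss was intended or could operate.

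A reader might also infer that the ITT rule is contradicted. It is not. "Subjects will be analyzed in the group to which they were randomized, regardless of compliance with the protocol or withdrawal from the study" sets group assignment, and withdrawn children stay in the sample and are censored.

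Two further objections narrow the point:
- Section 11.2 describes loss to follow-up as a state where no further contact is possible, and its consent item already covers follow-up. The children most clearly affected are those under item 4, and that item does not mention deterioration.
- One could read 11.4 as covering children who withdraw without being terminated. The protocol draws no such line, and 11.2 lists withdrawal as a reason for termination.

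What remains is the conflict between the termination clause and 11.4, 12.4 and 8.4, and the mismatch of triggers.

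**Conclusion.** The point holds as a conflict in the protocol that can cost primary endpoint data. Following the termination definition, a site stops reporting CAD, relisting and death for children who have not withdrawn consent. The same rule applies in both arms. The censoring is informative if termination is related to prognosis, which the documents neither show nor exclude.

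The size is unknown. One to two of about 21.6 expected events is an illustration that rests on the assumed 10–20% dropout, uniform dropout times, HR 0.40 and follow-up of 1 to 4.5 years. It overstates what a correction could recover, because some of those children would have withdrawn consent or be beyond reach. Arm-dependent bias and a contradiction of ITT should not be read into the text. The rituximab-only wording of 11.3 and 11.4 is most likely shorthand, but it needs correcting because its literal form cannot be applied under the blind and its trigger differs from that of ITT. The change is worth making because it is cheap and events are few.

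**What to change.** - In 11.3 and 11.4, replace the condition with: any portion of the first infusion of study drug (rituximab or placebo). This matches the ITT definition in both documents.
- In the Study Termination definition, limit the no-data clause to participants who withdraw consent for data collection, and reconcile it with 11.4, 12.4.1 and 12.4.3.
- For all other terminated participants, state that dates of CAD, relisting and death continue to be recorded from routine centre care to the end of follow-up, as 8.4 already implies.

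The cost is protocol wording and a few status checks at centres that already follow these children. The target stays at 50, and no dose, visit schedule or clinical rule changes.

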11.4. Follow-up after Early Study Withdrawal

Participants who receive at least one dose of rituximab will follow the schedule of events-Appendix 1.

12. Safety Monitoring and Reporting

12.1 Overview

This section defines the types of safety data that will be collected under this protocol and outlines the procedures for appropriately collecting, grading, recording, and reporting those data. Adverse events that are classified as serious according to the definition of health authorities must be reported promptly (per Section 12.5, *Reporting of Serious Adverse Events and Adverse Events*) to DAIT/NIAID. Appropriate notifications will also be made to site principal investigators, Institutional Review Boards (IRBs) and health authorities.

Information in this section complies with *ICH Guideline E2A: Clinical Safety Data Management: Definitions and Standards for Expedited Reporting*, *ICH Guideline E-6: Guideline for Good Clinical Practice*, 21CFR Parts 312 and 320, and applies the standards set forth in the National Cancer Institute (NCI), Common Terminology Criteria for Adverse Events (CTCAE), Version 4.0: <http://ctep.cancer.gov/reporting/ctc.html>.

12.2 Definitions

12.2.1 Adverse Event (AE)

Any untoward or unfavorable medical occurrence associated with the subject's participation in the research, whether or not considered related to the subject's participation in the research (modified from the definition of adverse events in the 1996 International Conference on Harmonization E-6 Guidelines for Good Clinical Practice) (from OHRP "Guidance on Reviewing and Reporting Unanticipated Problems Involving Risks to Subjects or Others and Adverse Events (1/15/07)"

<http://www.hhs.gov/ohrp/policy/advevtguid.html#Q2>)

For this study, an adverse event will include any untoward or unfavorable medical occurrence associated with:

- **Study therapy regimen:** Rituximab or Rituximab Placebo
- **Study mandated procedures:**
 - Bronchoscopy: Any AE occurring within 24 hours after a study related bronchoscopy.
 - Blood Draw: Any AE occurring within 24 hours after a study related blood draw.

12.2.1.1 Suspected Adverse Reaction (SAR)

Any adverse event for which there is a reasonable possibility that the investigational drug [or investigational study therapy regimen] caused the adverse event. For the purposes of safety reporting, 'reasonable possibility' means there is evidence to suggest a causal relationship between the drug and the adverse event. A suspected adverse reaction implies a lesser degree of certainty about causality than adverse reaction, which means any adverse event caused by a drug (21 CFR 312.32(a)).

12.2.2 Unexpected Adverse Event

An adverse event or suspected adverse reaction is considered "unexpected" if it is not listed in the Investigator Brochure or package insert or is not listed at the specificity, severity or rate of occurrence that has been observed; or is not consistent with the risk information described in the general investigational plan or elsewhere in the IND.

“Unexpected” also refers to adverse events or suspected adverse reactions that are mentioned in the Investigator Brochure or package insert as occurring with a class of drugs or as anticipated from the pharmacological properties of the drug, but are not specifically mentioned as occurring with the particular drug under investigation (21 CFR 312.32(a))

12.2.3 Serious Adverse Event (SAE)

An adverse event or suspected adverse reaction is considered “serious” if, in the view of either the investigator or DAIT/NIAID, it results in any of the following outcomes (21 CFR 312.32(a)):

1. Death.
2. A life-threatening event: An AE or SAR is considered “life-threatening” if, in the view of either the investigator or DAIT/NIAID, its occurrence places the subject at immediate risk of death. It does not include an AE or SAR that, had it occurred in a more severe form, might have caused death.
3. Inpatient hospitalization or prolongation of existing hospitalization.
4. Persistent or significant incapacity or substantial disruption of the ability to conduct normal life functions.
5. Congenital anomaly or birth defect.
6. Important medical events that may not result in death, be life threatening, or require hospitalization may be considered serious when, based upon appropriate medical judgment, they may jeopardize the subject and may require medical or surgical intervention to prevent one of the outcomes listed above.

The NIAID medical monitor will review each SAE and assess the relationship of the event to the study procedure. Events meeting serious criteria that occur outside of these parameters should also be reported if the investigator deems a possible association with a protocol mandated procedure. Elective hospitalizations or hospital admissions for the purpose of conduct of protocol mandated procedures are not to be reported as an SAE unless hospitalization is prolonged due to complications.

12.3 Grading and Attribution of Adverse Events

12.3.1 Grading Criteria

The study site will grade the severity of adverse events experienced by the study subjects according to the criteria set forth in the National Cancer Institute’s Common Terminology Criteria for Adverse Events (CTCAE) version 4. This document (referred to herein as the NCI-CTCAE manual) provides a common language to describe levels of severity, to analyze and interpret data, and to articulate the clinical significance of all adverse events. The NCI-CTCAE has been reviewed by the Protocol Chair and Principal Investigator and has been deemed appropriate for the subject population to be studied in this protocol.

Adverse events will be graded on a scale from 1 to 5 according to the following standards in the NCI-CTCAE manual:

Grade 1 = mild adverse event.

Grade 2 = moderate adverse event.

Grade 3 = severe and undesirable adverse event.

Grade 4 = life-threatening or disabling adverse event.

Grade 5 = death.

Events grade 1 and 2 will not be collected. Events grade 3 or higher will be recorded on the appropriate AE electronic case report form except for hematologic cytopenias. Only hematologic cytopenias meeting serious criteria outlined in 12.2.3 and occurring from the time of first rituximab infusion to 6 weeks following the last rituximab infusion will be collected and reported to the sponsor. Outside of this period, hematologic cytopenias meeting grade 3 and higher will be collected and reported to the sponsor.

For grading an abnormal value or result of a clinical or laboratory evaluation (including, but not limited to, a radiograph, an ultrasound, an electrocardiogram etc.), a treatment-emergent adverse event is defined as an increase in grade from baseline or from the last post-baseline value that doesn't meet grading criteria. Changes in grade from screening to baseline will also be recorded as adverse events, but are not treatment-emergent. If a specific event or result from a given clinical or laboratory evaluation is not included in the NCI-CTCAE manual, then an abnormal result would be considered an adverse event if changes in therapy or monitoring are implemented as a result of the event/result.

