b. Progressive multifocal leukoencephalopathy (PML): PML is a rare disease caused by the reactivation of latent JC virus in the brain. Immunosuppression allows reactivation of the JC virus which causes demyelination and destruction of oligodendrocytes resulting in death or severe disability. Rare cases of PML, some resulting in death, have been reported in patients with hematologic malignancies who have received rituximab. The majority of these patients had received rituximab in combination with chemotherapy or as part of a hematopoietic stem cell transplant. Cases of PML resulting in death have also been reported following the use of rituximab for the treatment of autoimmune diseases. The reported cases had multiple risk factors for PML, including the underlying disease and long-term immunosuppressive therapy or chemotherapy. Most cases of PML were diagnosed within 12 months of their last infusion of rituximab.

Physicians should consider PML in any patient presenting with new onset neurologic manifestations. Consultation with a neurologist, brain MRI, and lumbar puncture should be considered as clinically indicated. In patients who develop PML, rituximab should be discontinued and reductions or discontinuation of any concomitant chemotherapy or immunosuppressive therapy should be considered.

Hematologic Events: In clinical trials, Grade 3 and 4 cytopenias were reported in 48% of patients treated with rituximab; these include: lymphopenia (40%), neutropenia (6%), leukopenia (4%), anemia (3%), and thrombocytopenia (2%). The median duration of lymphopenia was 14 days (range, 1 to 588 days) and of neutropenia was 13 days (range, 2 to 116 days). A single occurrence of transient aplastic anemia (pure red cell aplasia) and two occurrences of hemolytic anemia following Rituximab therapy were reported.

In addition, there have been a limited number of postmarketing reports of prolonged pancytopenia, marrow hypoplasia, and late onset neutropenia.

Infectious Events: Rituxan® induced B cell depletion in 70% to 80% of patients with NHL and was associated with decreased serum immunoglobulins in a minority of patients; the lymphopenia lasted a median of 14 days (range, 1-588 days). Infectious events occurred in 31% of patients: 19% of patients had bacterial infections, 10% had viral infections, 1% had fungal infections, and 6% were unknown infections. Serious infectious events (Grade 3 or 4), including sepsis, occurred in 2% of patients.

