6.1.1.2. Dosage and Preparation

Rituximab will be given as an intravenous infusion.

2 Doses: 375 mg/m² on Day 0 (within 12 hours of return to ICU following transplant) and Day 12 (+/- 2 days).

Rituximab should be prepared using appropriate aseptic techniques. Withdraw the necessary amount of Rituximab or Rituximab Placebo and dilute to a final concentration of 1 to 4 mg/mL into an infusion bag containing either 0.9% Sodium Chloride, USP, or 5% Dextrose in Water, USP. Gently invert the bag to mix the solution. Discard any unused portion left in the vial. Parenteral drug products should be inspected visually for particulate matter and discoloration prior to administration.

Rituximab or Rituximab Placebo should be given as a **slow** intravenous infusion. **It should not be administered as an intravenous push or bolus.** Do not infuse rituximab concomitantly with another IV solution or other IV medications. Rituximab infusions should be made through a dedicated line.

Participants will be premedicated using:

- Tylenol® (Acetaminophen), 15 mg/kg (to a maximum of 1 gram) should be administered (by mouth, enteral or rectal administration) 30 to 60 minutes prior to the start of an infusion; and
- Benadryl® (Diphenhydramine) by mouth 30-60 minutes prior to the start of an infusion as described in **Table 1** or by IV 1 mg/kg (to a maximum of 50 mg) 30 minutes prior to the start of an infusion.

Age (years)	Diphenhydramine Oral Dose (mg)
2-6	6.25
6-<12	12.5
12+	25

Table 1: Diphenhydramine Pre-medication Dose

Premedication may attenuate infusion-related events. Since transient hypotension may occur during rituximab infusion, consideration should be given to withholding anti-hypertensive medications 12 hours prior to rituximab infusion.

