8.4. Clinical Laboratory Evaluation

Clinical laboratory measurements include serum chemistry and hematology. Results will be converted to standardized units where possible. For numeric laboratory results, descriptive statistics of laboratory values and the change from baseline of laboratory values will be summarized for each treatment group and overall. For any categorical laboratory results, the number and percentage of subjects reporting each result will be presented for each treatment group and overall.

In addition, or in lieu of summary statistics, clinical laboratory data may be plotted to show patterns over time. For each test with a numeric result, data will be plotted as a spaghetti plot where each subject's values will be plotted and connected by line segments, forming one line per subject. Tests with qualitative results will not be plotted.

Separate listings of laboratory data over time may also be created.

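### Non-serious grade 3–4 cytopenias are outside adverse-event collection until about day 54; the SAP does not say so and never counts children with severe blood values by arm

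*Protocol*

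**What the plan says.** Protocol 12.3.1 gives the general rule with its exception: "Events grade 3 or higher will be recorded on the appropriate AE electronic case report form except for hematologic cytopenias". Inside a defined window the entry condition is narrower: "Only hematologic cytopenias meeting serious criteria outlined in 12.2.3" are eligible. That window opens with the first infusion and closes six weeks after the final one. Elsewhere the usual threshold returns: "Outside of this period, hematologic cytopenias meeting grade 3 and higher will be collected and reported to the sponsor". Protocol 6.1.1.2 places the two infusions on day 0 and day 12, with two days' allowance on the second.

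SAP 8.2 says that the protocol collects AEs of grade 3 or higher and does not carry the cytopenia exception. It tabulates treatment-emergent events by arm, and Protocol 13.4.4 adds 90% confidence intervals to the AE summaries.

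Blood counts themselves are collected. Protocol Appendix 1 schedules a CBC with differential and platelets at day 0, day 12, weeks 4–6, month 2, later visits and unscheduled visits. Protocol 6.2 asks for a CBC before each infusion. SAP 8.4 states that "descriptive statistics of laboratory values and the change from baseline of laboratory values will be summarized" by treatment group, and it permits per-subject line plots and listings. Under the SAP 3 conventions the summary consists of n, mean, SD, median, minimum and maximum. No section assigns a CTCAE grade to a laboratory value or counts the children who reach grade 3–4.

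**The concern.** Safety and tolerability of rituximab is a stated secondary objective (Protocol 1.3), and cytopenia is among the drug's listed risks: Protocol 5.1 reports that "Grade 3 and 4 cytopenias were reported in 48% of patients treated with rituximab" in other populations, with median durations of 14 days for lymphopenia and 13 days for neutropenia.

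A non-serious grade 3 neutropenia on day 30 creates no AE record; the same event on day 70 does. Both periods feed the same row of the by-arm AE table. Someone working from SAP 8.2 would take that row as complete from the first infusion, and could read a small difference between arms as reassurance about a period in which most grades of event were not eligible to be counted.

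Monitoring has the same gap. Protocol 12.8.2.1 sets a listing of AEs and SAEs as the minimum for planned DSMB reviews, and no stopping rule concerns cytopenia. By contrast, SAP 7.3.2 deals openly with the AE restriction for infections: those not reported as AEs are kept and assigned a grade below 3. Cytopenias get no equivalent.

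**Working it through.** The plan states no figure on this point, so there is none to reproduce. The check is date arithmetic, a comparison of data sources, and an illustration on stated assumptions.

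**1. Length of the window.** End day = day of last infusion + 42 (Protocol 12.3.1 and 6.1.1.2).
- Second infusion on day 12: 12 + 42 = day 54, or 54/365 = 14.8% of the minimum follow-up.
- With the ±2-day allowance: 10 + 42 = day 52 to 14 + 42 = day 56.
- First infusion only: 0 + 42 = day 42.

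**2. Scheduled CBCs inside it** (Protocol Table 11 and Appendix 1).
- Day 12 ± 2: days 10 to 14.
- Weeks 4–6, +6/−7 days: 28 − 7 = day 21 to 42 + 6 = day 48.
- Month 2 ± 7 days, taking 2 × 30.4 ≈ 61: days 54 to 68, so mostly after the window closes.

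The scheduled post-dose counts in the window are therefore mainly day 12 and weeks 4–6. If the day-12 count is the pre-infusion count required by Protocol 6.2, only one scheduled count follows the second infusion. The gap between the two visits runs from 21 − 14 = 7 days to 48 − 10 = 38 days. An episode of 13 to 14 days fits inside the window and can fall between the two counts.

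**3. Where a non-serious grade 3–4 cytopenia appears.**

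| Onset | AE tables by arm | SAP 8.4 summary | Count of children affected |
|---|---|---|---|
| First infusion to about day 54 | No | Only as a value at a collected visit | None planned |
| Later | Yes | Only as a value at a collected visit | Through the AE tables |

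**4. Illustration of the loss.** Assumptions: the 48% in Protocol 5.1 applies to 25 rituximab children; the control rate is 24%; the same share *s* of affected children in each arm have only non-serious, in-window events. The documents give neither the control rate nor *s*. Captured children on rituximab = 25 × 0.48 × (1 − *s*). Captured risk difference = 0.24 × (1 − *s*). Power is for two proportions, 25 per arm, two-sided 0.10 to match the 90% interval.

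| *s* | Captured on rituximab | Risk difference | Power |
|---|---|---|---|
| 0 | 12 | 0.24 | 0.55 |
| 0.25 | 9 | 0.18 | 0.42 |
| 0.50 | 6 | 0.12 | 0.29 |
| 0.75 | 3 | 0.06 | 0.18 |
| 0.90 | 1.2 | 0.02 | 0.12 |

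**5. What complete counting could show.** Under the same rates, the 90% half-width for the risk difference is 1.645 × √[(0.48 × 0.52 + 0.24 × 0.76)/25] = 1.645 × √(0.432/25) = 0.22, giving 0.24 ± 0.22. By lineage, the Protocol 5.1 rates imply 25 × 0.40 = 10 children with lymphopenia, 25 × 0.06 = 1.5 with neutropenia, 25 × 0.03 = 0.75 with anemia and 25 × 0.02 = 0.5 with thrombocytopenia.

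**The case against.** The strongest reply is that the counts are not hidden. They are collected and summarized by arm, and the minimum reported under SAP 3 shows the lowest value in each group; plots and listings can show individual children. This stands, and it rules out any reading that early cytopenias go wholly unrecorded. But a minimum describes one child and does not say how many were severe, and the plots and listings are optional.

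Second, the clinically weightier events remain. Serious cytopenias are collected throughout, with prolonged hospitalization and important medical events among the criteria in Protocol 12.2.3. Infections are analysed at all grades. Cytopenia is not a named safety endpoint. All of this stands and limits the importance of the point.

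Third, every child receives Thymoglobulin and MMF, which carry cytopenia risks of their own, and much of the 48% is lymphopenia, largely an expected effect of B-cell depletion. That could justify limiting AE reports, although the protocol gives no reason for the exception. It does not justify omitting a by-arm count, because a background shared by both arms is what randomization separates from the drug. The B- and T-cell fractions compared in SAP 7.4 do not cover neutrophils, platelets or severity.

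Fourth, two scheduled counts recover only part of what is missing. This stands, and is a stated limit of the fix.

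**Conclusion.** The point holds in a limited form. For about the first eight weeks (to day 54; day 42 after one dose) the AE tables cannot compare non-serious grade 3–4 cytopenias between arms. The SAP does not disclose this, and no other planned output counts the children affected. It is an inexpensive improvement to safety reporting and does not touch the primary analysis.

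A reader might infer more, but the documents do not support it:
- **That the window is exactly when rituximab acts.** Protocol 2.1 puts B-cell repopulation at 3–6 months, and Protocol 5.1 mentions late onset neutropenia. Both reach into the period of full collection.
- **That most drug-related episodes fall inside the window.** Protocol 5.1 gives durations, not onset times. Its ranges extend to 116 days for neutropenia and 588 days for lymphopenia.
- **That the rule favours rituximab.** Protocol 12.3.1 refers only to rituximab infusions, but blinded site staff could not apply an arm-specific window. It presumably covers both arms, so what is shown is lost information.

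The size of the loss depends on the in-window, non-serious share and on the control rate, neither of which is stated. The illustrative range is 1.2 to 9 of 12 children still captured. The 48% comes from other populations.

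**What to change.** 1. Leave the AE collection rule as it is.
2. In SAP 8.2, state the cytopenia exception and its window, defined by the blinded study infusion in either arm. Footnote the AE tables so that cytopenia rows are read as serious-only inside the window and grade 3 or higher outside it.
3. In SAP 8.4, derive CTCAE version 4 grade 3–4 neutropenia, lymphopenia, anemia and thrombocytopenia from the scheduled and unscheduled CBCs. For each lineage and arm, tabulate the proportion of children affected through month 2, with the risk difference and 90% confidence interval. Keep lineages separate, since lymphopenia would otherwise dominate.

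The cost is one derived table, a sentence and a footnote. No new data are needed, provided the CBC results in Appendix 1 are held in the database, as SAP 8.4 implies. Inside the window the scheduled post-dose counts are mainly day 12 and weeks 4–6, so short episodes between visits will be missed and the proportions will be lower bounds. Intervals will be wide, and for the rarer lineages the table will be essentially descriptive.
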